9.1.8. Case Report Forms

For each participant consented, an eCRF casebook will be completed by an authorized study staff member whose training for this function is completed in the electronic data capture (EDC) system. The eCRF casebook will only capture the data required per the protocol schedule of events and procedures. The Inclusion/Exclusion Criteria and Enrollment eCRFs should be completed only after all data related to eligibility have been received. Data entry should be performed in accordance with the eCRF Completion Guidelines provided by the sponsor. After data entry, a study monitor will perform source data verification within the EDC system. System-generated or manual queries will be issued in the EDC system as data discrepancies are identified by the monitor or Gilead staff, who routinely review the data for completeness, correctness, and consistency. The site investigator or site coordinator or other designee is responsible for responding to the queries in a timely manner, within the system, either by confirming the data as correct or updating the original entry, and providing the reason for the update (eg, data entry error). Original entries as well as any changes to data fields will be stored in the audit trail of the system. At a minimum, prior to any interim time points or database lock (as instructed by Gilead), the investigator will use his/her log in credentials to confirm that the forms have been reviewed, and that the entries accurately reflect the information in the source documents. At the conclusion of the study, Gilead will provide the site investigator with a read-only archive copy of the data entered by that site. This archive must be stored in accordance with the records retention requirements outlined in Section 9.1.7.

9.1.9. Investigator Inspections

The investigator will make available all source documents and other records for this study to Gilead's appointed study monitors, to IRBs/IECs, or to regulatory authority or health authority inspectors.

9.1.10. Protocol Compliance

The investigator is responsible for ensuring the study is conducted in accordance with the procedures and evaluations described in this protocol.

9.2. Sponsor Responsibilities

9.2.1. Protocol Modifications

Protocol modifications, except those intended to reduce immediate risk to study participants, may be made only by Gilead. The investigator must submit all protocol modifications to the in accordance with local requirements and receive documented approval before modifications can be implemented.

9.2.2. Study Reports and Publications

A CSR will be prepared and provided to the regulatory agency(ies) when applicable and in accordance with local regulatory requirements. Gilead will ensure that the report meets the standards set out in the ICH Guideline for Structure and Content of Clinical Study Reports (ICH E3). Note that an abbreviated report may be prepared in certain cases. For studies with sites in countries following the Directive 2001/20/EC, a CSR will be submitted within 1 year (6 months for pediatric studies, in accordance with Regulation [EC] No. 1901/2006) after the global end of study (as defined in Section 6.8).

Investigators in this study may communicate, orally present, or publish in scientific journals or other scholarly media in accordance with the Gilead clinical trial agreement. Study results will be made publicly available (including posted to the Clinical Trials Information System and ClinicalTrials.gov) in accordance with local regulatory requirements.

9.3. Joint Investigator/Sponsor Responsibilities

9.3.1. Payment Reporting

Investigators and their study staff may be asked to provide services performed under this protocol, eg, attendance at investigator meetings. If required under the applicable statutory and regulatory requirements, Gilead will capture and disclose to Federal and State agencies any expenses paid or reimbursed for such services, including any clinical study payments, meal, travel expenses or reimbursements, consulting fees, and any other transfer of value.

9.3.2. Access to Information for Monitoring

The monitor is responsible for routine review of the eCRF at regular intervals throughout the study to verify adherence to the protocol and the completeness, consistency, and accuracy of the data being entered on them. The monitor should have access to any participant records needed to verify the entries in the eCRF. The investigator agrees to cooperate with the monitor to ensure that any problems detected through any type of monitoring (central, on site) are resolved.

9.3.3. Access to Information for Auditing or Inspections

Representatives of regulatory authorities or of Gilead may conduct inspections or audits of the clinical study. If the investigator is notified of an inspection by a regulatory authority the investigator agrees to notify the Gilead medical monitor immediately. The investigator agrees to provide to representatives of a regulatory agency or Gilead access to records, facilities, and personnel for the effective conduct of any inspection or audit.

9.3.4. Study Discontinuation

Both Gilead and the investigator reserve the right to terminate the study at any time. Should this be necessary, both parties will arrange discontinuation procedures and notify the participants, appropriate regulatory authorities, IRBs, and IECs. In terminating the study, Gilead and the investigator will assure that adequate consideration is given to the protection of the participants' interests.

9.3.5. Data Protection

Enterprise level technical and organizational controls have been developed at Gilead for the purpose of data protection. This includes user authentication and identification, fine grained access controls, end-to-end data encryption, security monitoring, network segregation, and physical security controls. Users of Gilead systems are provided training for security awareness and privacy.

To prepare for the possibility of a data security breach, Gilead maintains a business continuity and disaster recovery plan and conducts regular disaster recovery testing to ensure that Gilead systems are recoverable if a cyber or data security incident is experienced. Gilead's detailed incident response plan for any cyber or data security incident is based on the following 5 steps: detection, analysis, containment, eradication, and recovery. Gilead's standard clinical trial agreement with study sites also includes data privacy language and arrangements in case of data security breaches as follows:

Gilead and institutions will both act in accordance with the applicable data protection law. Furthermore, the study site and Gilead will cooperate with each other to take the necessary measures in order to comply with the applicable data protection law. Both Gilead and the study site shall implement appropriate technical and organizational measures to meet the requirements of the EU General Data Protection Regulation. If either party becomes aware of a personal data breach related to data processed under this agreement, that party shall promptly notify the other party. In such a case, parties will fully cooperate with each other to remedy the personal data breach and promptly fulfill the (statutory) notification obligations. A personal data breach refers to a personal data breach as described in Article 4, Article 33, and Article 34 of the EU General Data Protection Regulation and applicable national data protection laws.

Appendix 2. Study Procedures Table

	Screening ^a	Cohort Selection ^b	Day 1 ^c	Day 2	Day 5	Day 8	Day 15 ^d	Day 16 ^d	Day 19 ^d	Day 22 ^d	Day 1 SC	Weeks 4, 10, 16, 22, 26, 36	Week 52 and Visits Thereafter ^e	Oral Bridging Visits ^f	Week 156 and Visits Thereafter ^g	30, 90, and 180 Day Follow-Up ^h	Early Termination ⁱ
Written Informed Consent/Assent/Parental Consent	X																
Medical History	X																
Demographic Information	X																
Complete Physical Examination	X		X				X				X	X ^j	X ^j				X
Symptom-Directed Physical Examination				X		X		X		X		X ^j	X ^j	X	X ^j	X	
Vital Signs (include weight) ^k	X		X	X		X	X	X		X	X	X	X	X	X	X	X
12-lead ECG (supine)	X																
Height	X																
Hematology ^l , Chemistry ^m , Estimated GFR, Urinalysis ⁿ , Urine Chemistry ⁿ , CD4+ Cell Count	X		X			X	X			X	X	X	X	X	X	X	X
Urine Storage Sample			X	X		X	X	X		X	X	X	X	X			X
Serum Pregnancy Test ^o	X																
Serum FSH ^p	X																
Urine Pregnancy Test ^o			X			X	X			X	X	X	X	X	X	X	X
HBV, HCV Testing	X																
HIV-1 Genotyping/Phenotyping	X																
Plasma HIV-1 RNA	X	X	X	X		X	X	X		X	X	X	X	X	X	X	X
Plasma Storage Sample	X	X	X	X		X	X	X		X	X	X	X	X		X	X
Intensive PK Plasma Collection ^q			X				X										

[figure not shown]
	Screening ^a	Cohort Selection ^b	Day 1 ^c	Day 2	Day 5	Day 8	Day 15 ^d	Day 16 ^d	Day 19 ^d	Day 22 ^d	Day 1 SC	Weeks 4, 10, 16, 22, 26, 36	Week 52 and Visits Thereafter ^e	Oral Bridging Visits ^f	Week 156 and Visits Thereafter ^g	30, 90, and 180 Day Follow-Up ^h	Early Termination ⁱ
Single Timed, Single Anytime, and/or Predose PK Plasma Sample ^f				X	X	X		X	X	X	X	X ^{s,t}	X	X			
Optional Whole Blood Sample for PG ^u			X														
Oral LEN Administration ^v			X	X		X	X	X		X				X			
Begin OBR ^w			X				X				X						
SC LEN Administration ^x											X	X	X		X		
Symptoms Distress Module, SF-36, EQ-5D-5L ^y			X									X	X				
Numeric Pain Scale ^z											X	X	X				
Injection Site Reaction Worksheet ^{aa}											X	X	X				
Adverse Events/Concomitant Medications	X	X	X	X	X	X	X	X	X	X	X	X	X	X	X ^{bb}	X	X

AE = adverse event; ALT = alanine aminotransferase; ARV = antiretroviral; AST = aspartate aminotransferase; BUN = blood urea nitrogen; CBC = complete blood count; CD4 = clusters of differentiation 4; CK = creatine kinase; ECG = electrocardiogram; EQ-5D-5L = EuroQol (5 dimensions, 5 levels); FSH = follicle-stimulating hormone; GFR = glomerular filtration rate; GGT = gamma-glutamyl transferase; HBV = hepatitis B virus; HCV = hepatitis C virus; HIV-1 = human immunodeficiency virus type 1; IEC = independent ethics committee; IRB = institutional review board; LDH = lactate dehydrogenase; LEN = lenacapavir; OBR = Optimized Background Regimen; PG = pharmacogenomics; PK = pharmacokinetic(s); RNA = ribonucleic acid; SC = subcutaneous; SF-36 = Short Form-36

- a Screening evaluations must be completed within 42 days prior to Day 1.
- b Cohort Selection visit to be completed 14 to 30 days after the screening visit until Cohort 1 is fully enrolled.
- c Day 1 tests and procedures must be completed prior to study drug administration.
- d Days 15, 16, 19, and 22 visits will be completed by Cohort 1B participants only.
- e At the Week 52 visit, participants will be given an option to attend visits at Weeks 62, 78, 88, 104, 114, 130, and will continue to alternate between every 10 weeks and every 16 weeks. Participants will receive SC LEN every 6 months (26 weeks) ± 2 weeks from last injection starting at Week 52 visit, while continuing their OBR, until the product becomes accessible to participants through an access program, is commercially available, or until Gilead elects to discontinue the study in the country.
- f Only applicable to participants who require oral weekly bridging if an SC injection of LEN cannot be administered for any reason within the protocol visit window.
- g At Week 156 and thereafter, upon regulatory and/or IRB/IEC approval of the protocol and when participants have provided written informed consent of the most current IRB-approved consent form, participants will continue to receive study drug every 26 weeks, and continue to attend visits every 26 weeks (± 2 weeks). Participants will receive SC LEN every 6 months (26 weeks) ± 2 weeks from the last injection starting at the Week 156 visit, while continuing their OBR, until the product becomes accessible to participants through an access program, is commercially available, or until Gilead elects to discontinue the study in the country.
- h Participants may be required to return to the clinic for a 30-, 90-, and 180-day follow-up visit after early termination visit as noted in Section 6.4.1.
- i Early termination visit to be completed, if participant decides to discontinue study drug prior to completing Week 52 visit or prior to study completion. Investigators should counsel participant regarding the importance of continuing a complete ARV therapy in accordance to standard of care, and refer participant to an appropriate HIV treatment facility.

- j Complete physical examination to be completed at Weeks 26, 52, and 156, symptom-directed physical examination to be completed at all other visits.
- k Vital signs: blood pressure, pulse, respiration rate, and temperature, weight.
- l Hematology: CBC with differential and platelet count.
- m Chemistries: alkaline phosphatase, AST, ALT, GGT, total bilirubin, direct and indirect bilirubin, total protein, albumin, LDH, CK, bicarbonate, BUN, calcium, chloride, creatinine, glucose, lipase, magnesium, phosphorus, potassium, sodium, uric acid (except at Cohort Selection, Days 2, 5, 16, and 19 visits).
- n Urinalysis and Urine Chemistry: including color & clarity, specific gravity, pH, glucose, ketones, bilirubin, urobilinogen, blood, nitrite, leukocyte esterase and microscopic (if microscopic elements are seen), urine protein, albumin, creatinine, phosphate, calcium, magnesium and uric acid (except at Cohort Selection, Days 2, 5, 16, and 19 visits).
- o All women will have a serum test performed at screening. Urine pregnancy test will be performed at all subsequent visits for women of childbearing potential (except at Days 2, 5, 16, and 19). Positive urine pregnancy tests will be confirmed with a serum test.
- p FSH test is required for women who are < 54 years old and have stopped menstruating for ≥ 12 months but do not have documentation of ovarian hormonal failure.
- q Day 1 (for all participants) and Day 15 (for Cohort 1B participants only): 0 (predose, ≤ 30 min before dose), 1, 2, 4, 6, and 8 hours postdose.
- r Days 2, 8, 16, and 22: A predose sample (within 30 minutes of dosing) and a single timed PK samples between 1 and 6 hours postdose. Days 5 and 19 (if the visits are completed): a single anytime PK sample.
- s During the Maintenance Period, at all visits without SC LEN injections, including the Oral Bridging visits, if applicable: A single anytime PK sample will be collected.
- t During the Maintenance Period, at all visits with SC LEN injections: A single predose (within 30 minutes of dosing) PK sample will be collected (while participants are continuing to receive study drug).
- u If consent for pharmacogenomic testing is obtained, then a sample will be collected for optional pharmacogenomic testing. This sample should be collected at the Day 1 visit, but may be collected at any time during the study or at a separate poststudy visit, if necessary.
- v Cohort 1 participants will be administered oral LEN or placebo to match LEN at Days 1, 2, and 8. Participants who receive placebo to match LEN at Days 1, 2, and 8 will receive oral LEN at Days 15, 16, and 22. Cohort 2 participants will be administered oral LEN at Days 1, 2, and 8. Participants requiring oral bridging will be administered oral LEN per Section 5.4, as applicable.
- w Cohort 1 participants will begin an OBR on Day 15 (Cohort 1B) or Day 1 SC (Cohort 1A). Cohort 2 participants will begin an OBR on Day 1. An OBR should be selected based on the screening and/or available historical HIV resistance reports.
- x All participants will be administered SC LEN at Day 1 SC (14 days after the first dose of oral LEN) and will continue to receive SC LEN every 6 months (26 weeks) ± 2 weeks from last injection. Each SC LEN dosing should occur 6 months (26 weeks) ± 2 weeks from last injection.
- y Participants ≥ 18 years of age at Day 1 visit will complete Symptoms Distress Module, SF-36, EQ-5D-5L at Day 1, Weeks 4, 16, 26, and 52, if available (before completing other study procedures).
- z Participants ≥ 18 years of age at Day 1 visit will complete the Numeric Pain Rating Scale at Day 1 SC, Weeks 26 and 52 (after they receive SC LEN injections).
- aa Provide injection site reaction assessment worksheet and instruct the participants to measure and report injection site reactions following the administration of the SC injections.
- bb For visits after Week 156, it is recommended that a phone contact to the participant is made in between in-clinic visits (ie, every 13 weeks) to assess for any AEs experienced by the participant.

Appendix 3. Management of Clinical and Laboratory Adverse Events

Appendix 4. Pregnancy Precautions, Definition for Women of Childbearing Potential, and Contraceptive Requirements

1) Definitions

a. Definition of Childbearing Potential

For the purposes of this study, a female born participant is considered a woman of childbearing potential following the initiation of puberty (Tanner stage 2) until becoming postmenopausal, unless permanently sterile or with medically documented ovarian failure. For participants deemed by the investigator to have initiated puberty, no documentation of Tanner stage will be required.

Female born participants are considered to be in a postmenopausal state when they are ≥ 54 years of age with cessation of previously occurring menses for ≥ 12 months without an alternative cause. In addition, female born participants < 54 years of age with amenorrhea of ≥ 12 months may also be considered postmenopausal if their follicle-stimulating hormone level is in the postmenopausal range and they are not using hormonal contraception or hormonal replacement therapy.

For the purposes of this study, permanent sterilization is hysterectomy, bilateral oophorectomy, or bilateral salpingectomy in a female born participant of any age. Tubal ligation is not considered permanent sterilization.

b. Definition of Male Fertility

For the purposes of this study, a male born participant is considered fertile after the initiation of puberty unless permanently sterile by bilateral orchidectomy or medical documentation.

2) Contraception Requirements for Female Born Participants

a. Study Drug Effects on Pregnancy and Hormonal Contraception

Nonclinical toxicity studies of lenacapavir (LEN; GS-6207) have demonstrated no adverse effect on fertility or embryo-fetal development. However, there are no clinical studies of LEN in pregnant women. Based on in vitro and in vivo drug-drug interaction liability assessment, a clinically significant drug-drug interaction with LEN and hormonal contraceptives is not expected; an oral contraception drug-drug interaction study was not done.

b. Contraception Requirements for Female Born Participants of Childbearing Potential

The inclusion of female born participants of childbearing potential requires using at least an acceptable effective contraceptive. They must have a negative serum pregnancy test at screening and a negative pregnancy test at the Day 1 visit prior to the dose of study drug. Pregnancy tests will be performed as defined by the Study Procedures Table ([Appendix 2](#)). In the event of a delayed menstrual period (over 1 month between menstruations), a pregnancy test must be performed to rule out pregnancy. This is also applicable for female born participants of childbearing potential with infrequent or irregular periods.

Duration of contraception for female born participants of childbearing potential enrolled in this clinical trial should start from screening visit until 60 days after the last dose of oral study drug or 700 days following the last dose of subcutaneous (SC) study drug, whichever is later, as applicable.

Female born participants of childbearing potential must agree to 1 of the following contraceptive methods:

Complete abstinence from intercourse of reproductive potential. Abstinence is an acceptable method of contraception only when it is in line with the participant's preferred and usual lifestyle.

Or

- Consistent and correct use of 1 of the following methods of birth control listed below:
 - Hormonal and nonhormonal intrauterine device (IUD)
 - Bilateral tubal occlusion sterilization (upon medical assessment of surgical success)
 - Vasectomy in the male born partner (upon medical assessment of surgical success)

Or

Female born participants who initiate use of a hormonal contraceptive > 7 days after onset of menses as one of their birth control methods should use additional back-up contraception (eg, condoms) or avoid sexual intercourse for 7 days. Hormonally-based contraceptives and barrier methods permitted for use in this protocol are as follows:

— Hormonal Methods

- Oral contraceptives (either combined or progesterone only)
- Injectable progesterone^a
- Subdermal contraceptive implant^a
- Transdermal contraceptive patch^a
- Contraceptive vaginal ring^a

— Barrier methods

- Male condom (with or without spermicide)
- Female condom (with or without spermicide)
- Diaphragm with spermicide^a

- Cervical cap with spermicide^a
- Sponge with spermicide

^a Not approved in Japan.

Inclusion of methods of contraception in this list of permitted methods does not imply that the method is approved in any country or region. Methods should only be used if locally approved.

Female born participants must also refrain from egg donation and in vitro fertilization during treatment and until the end of contraception requirement.

3) Contraception Requirements for Male Born Participants

No contraception measures are needed.

Condoms should be used for all sexual activity including oral, vaginal, and anal sexual contact to decrease the risk of transmission of HIV and other sexually transmitted diseases.

4) Unacceptable Birth Control Methods

Birth control methods that are unacceptable include periodic abstinence (eg, calendar, ovulation, symptothermal, postovulation methods), withdrawal (coitus interruptus), spermicides only, and lactational amenorrhea method (LAM). A female condom and a male condom should not be used together.

5) Procedures to be Followed in the Event of Pregnancy

Female born participants who are pregnant or suspect they are pregnant will be instructed to notify the investigator at any time during the study and within 700 days following the last dose of SC LEN, or 60 days following the last oral dose of LEN. Male participants whose partner has become pregnant or suspects she is pregnant during the study, including the protocol-defined posttreatment follow-up period, must report the information to the investigator. Female born participants who become pregnant or who suspect that they are pregnant during the study should discontinue study drug immediately. Instructions for reporting pregnancy, partner pregnancy, and pregnancy outcome are outlined in Section [7.7.2.1](#).

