1.6. Risk/Benefit Assessment for the Study

Potential risks associated with the study include unknown adverse events (AEs), including ISRs, general risks associated with frequent clinic visits and laboratory blood draws, and the associated pain and discomfort of multiple phlebotomies. Although not specifically evaluated yet, adolescents living with HIV are expected to have similar safety profile as adult PWH; no additional safety monitoring is required for adolescent participants and no dose adjustments are required. Strategies to mitigate any potential risks include close monitoring of laboratory values as well as AEs. Parameters for monitoring of AEs will be well defined and closely followed.

In addition, potential risks to PWH include prolonged exposure to subtherapeutic concentrations of LEN if dosing is stopped which could lead to HIV-1 developing resistance to LEN. Strategies to mitigate any potential risks include initiation of an OBR within 15 days of starting LEN (Cohort 1) or co-initiation of LEN and an OBR (Cohort 2).

People with HIV are eligible for participation in this study if they are HTE with limited therapeutic options from the 4 main classes of ARV agents and inability to construct a fully active ARV regimen. Lenacapavir offers the potential benefit to construct a highly active regimen able to suppress HIV-1 replication, restoring or preserving immunologic function, and averting disease progression to AIDS. Given the above, the benefit-risk balance for this study is considered positive.

An unanticipated event such as a disaster or public health emergency may pose additional risks to study drug availability, the study visit schedule, and adherence to protocol-specified safety monitoring or laboratory assessments. Refer to [Appendix 5](#) for further details on the risks and risk mitigation strategy.

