6.5.3. Urine Samples

Urine samples will be collected for the following laboratory analyses at every study visit, unless otherwise specified:

- Urinalysis and urine chemistry: including color & clarity, specific gravity, pH, glucose, ketones, bilirubin, urobilinogen, blood, nitrite, leukocyte esterase and microscopic (if microscopic elements are seen), urine protein, albumin, creatinine, phosphate, calcium, magnesium and uric acid (except at Cohort Selection visit, Days 2, 5, 16, and 19 visits).
- Urine pregnancy test for women of childbearing potential (except at screening, Cohort Selection visit, Days 2, 5, 16, and 19 visits).
 - If the test is positive, confirmatory serum test should be performed and study drug dosing should be delayed until results obtained.
- Urine storage for possible additional clinical testing (except at screening, Cohort Selection, Day 5, Day 19, and at 30-, 90-, and 180-day follow-up visits, as applicable).

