6.6. Criteria for Discontinuation of Study Treatment

Study drug may be discontinued in the following instances:

- Intercurrent illness that would, in the judgment of the investigator, affect assessments of clinical status to a significant degree. Following resolution of intercurrent illness, the participant may resume study drug at the discretion of the investigator.
- Unacceptable toxicity, or toxicity that, in the judgment of the investigator, compromises the ability to continue study-specific procedures or is considered to not be in the participant's best interest.
- Lack of Efficacy; participants may continue to receive study drug if the investigator believes that there is medical benefit in doing so.
- Participant request to discontinue for any reason.
- Participant noncompliance.
- Pregnancy during the study; refer to [Appendix 4](#).
- Discontinuation of the study at the request of Gilead, a regulatory agency, or an IRB or IEC.

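### An unconfirmed positive urine pregnancy test falls under two conflicting study drug instructions: hold dosing until the serum result (Protocol 6.5.3), or discontinue at once on suspicion (Protocol Appendix 4, item 5)

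*Protocol*

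**What the plan says.** Five places in the protocol bear on this.

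- **Section 6.5.3 (urine samples):** "If the test is positive, confirmatory serum test should be performed and study drug dosing should be delayed until results obtained".
- **Appendix 2, note o:** "Positive urine pregnancy tests will be confirmed with a serum test". The note does not say what happens to study drug meanwhile. The SAP's copy of the schedule carries the same note.
- **Appendix 4, item 2b:** after a delayed period, "a pregnancy test must be performed to rule out pregnancy". This also covers infrequent or irregular periods. Study drug is not mentioned.
- **Appendix 4, item 5:** "Female born participants who become pregnant or who suspect that they are pregnant during the study should discontinue study drug immediately".
- **Section 6.6:** the list opens with "Study drug may be discontinued in the following instances". One entry is "Pregnancy during the study; refer to" Appendix 4.

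Section 6.4.1.2 sets an early termination visit within 72 hours of a decision to stop SC LEN between Day 1 SC and Week 52. Section 6.4.1.1 sets the same interval for stopping oral LEN before Day 1 SC.

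**The concern.** Sections 6.5.3 and Appendix 4 item 5 are both operative instructions, and they give different answers on the same facts. One treats an unconfirmed result as a reason to wait. The other treats suspicion as a reason to stop. Two sites following the protocol carefully could therefore act differently.

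The choice has consequences in both directions. Section 1.6 names as a risk "prolonged exposure to subtherapeutic concentrations of LEN if dosing is stopped which could lead to HIV-1 developing resistance to LEN", and this population has few alternative drugs. Against that, Appendix 4 item 2a notes that LEN has not been studied clinically in pregnant women. The protocol should not leave the decision to whichever section a site happens to read.

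There is also a data consequence. A discontinuation sets off early termination procedures and may be entered as a premature stop. A hold does neither.

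**Working it through.** The plan states no figure on this point, so the main check sets the provisions side by side for each situation.

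| Situation | 6.5.3 and Appendix 2 note o | Appendix 4 item 2b | Appendix 4 item 5 | 6.6 |
|---|---|---|---|---|
| Late period, no test yet | No instruction on dosing | Test; silent on study drug | Stop at once if she suspects pregnancy | Not covered |
| Positive urine test, serum pending | Serum test; 6.5.3 holds dosing | Not covered | Stop at once if the result makes her suspect pregnancy | Not covered |
| Serum negative | The wait ends; nothing further | Not covered | Silent on restart | Restart sentence covers intercurrent illness only |
| Pregnancy confirmed | The wait ends; nothing further | Not covered | Stop at once | May stop; see Appendix 4 |

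The second row holds the conflict. It rests on one inference: a participant with a positive urine test suspects she is pregnant. The protocol does not define the term, but the inference is hard to avoid. Reading the rules as successive steps (hold, confirm, then stop) does not remove the conflict, because item 5 attaches its instruction to suspicion itself.

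**Where it takes effect.** SC LEN is given on site every 26 weeks, so between injections there is usually no dose to hold or stop. Appendix 2 places urine tests at Days 1, 8, 15 and 22, Day 1 SC, the later scheduled visits (which include the injection visits) and the Oral Bridging visits. A test and a dose can therefore fall together. During weekly bridging most doses are taken at home (Section 5.4), so a participant could act on her own suspicion.

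**Whether a snapshot result can change.** SAP 6.2.1 counts HIV-1 RNA as on treatment up to 28 weeks after the last SC dose: 28 × 7 = 196 days. SAP Table 3-1 gives nominal days 379 (Week 52), 561 (Week 78) and 743 (Week 104), and a Week 104 window of Days 688 to 778. Assuming nominal visit dates:

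- *Hold or stop at Week 104, last injection at Week 78:* on treatment to 561 + 196 = Day 757. RNA drawn on Day 743 counts under either reading.
- *Hold at Week 78, injection given by the end of the 28 weeks since Week 52:* that limit is 379 + 196 = Day 575, which is 14 days after Day 561. On treatment then runs to 575 + 196 = Day 771, so Day 743 RNA counts.
- *Stop at Week 78 and never reversed:* on treatment ends on Day 575, before Day 688. There is then no on-treatment RNA in the window. Section 7.7.2.1 says pregnancy itself is not an AE, so the stop falls under other reasons, and the last on-treatment RNA decides between the 50-or-above category and no virologic data.

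A change in a Week 104 result therefore needs a stop that stays in force from about Week 78 or earlier. A short hold does not produce one.

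**The case against.** The strongest reply is that this is one loose word in an appendix and sites would manage. Most of the supporting points stand.

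- While the serum result is pending, both instructions usually mean that no dose is given.
- Item 5 does not say the stop is permanent. Sections 7.6.2 and 7.6.3 show that the protocol can distinguish withholding from permanent discontinuation.
- There is a general route back to dosing. Section 5.3 lets a participant dosed outside the window continue with the medical monitor's approval. Section 5.4 allows oral dosing when an injection cannot be given for any reason, including beyond 28 weeks. Neither is specific to pregnancy.
- SAP Appendix 3 classes a Main Phase participant as discontinued only when the Study Drug Completion form is marked No, and as continuing while it is blank. A hold with no form entered is already handled in that phase.
- The amendment history for Amendment 5 reports 13 participants remaining, so future exposure to the wording is limited.

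These points limit the consequences. They do not say which instruction governs an unconfirmed positive test, nor when a site should treat suspicion as a decision to discontinue.

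**Conclusion.** The conflict between Section 6.5.3 and Appendix 4 item 5 is real and minor. It rests on the plain wording of both and on the inference that a positive urine test creates suspicion.

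A reader might infer more than the documents support:

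- *Three competing rules for a possible pregnancy.* Section 6.6 is not a third rule. Its entry covers pregnancy, not suspicion; its permissive verb heads a general list; and it defers to Appendix 4. What remains is a secondary difference in force, for pregnancy itself, between an optional stop and an immediate one.
- *A late period only delays a dose at some sites.* Item 2b answers a late period with a test and is silent on study drug. The hold in 6.5.3 begins only after a positive urine test.
- *A false-positive test ends LEN for good.* Item 5 does not say so, and Sections 5.3 and 5.4 leave a way back.
- *A percentage effect on the endpoint.* The documents give neither the number of participants of childbearing potential nor a false-positive rate. One participant's weight in a proportion is not an estimate of what this wording would do.

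**What to change.** Reconcile Section 6.5.3 and Appendix 4 items 2b and 5 into one sequence that covers suspicion, a positive urine test and confirmed pregnancy in turn. Align the verb in Section 6.6 with it. State how a hold pending confirmation differs from a discontinuation: whether it calls for an early termination visit, whether the Study Drug Completion form stays blank, and what happens to dosing once pregnancy is excluded. The eCRF guidance should say the same for the Extension Phase, because SAP Appendix 3 spells out the form-based rule for the Main Phase only. Which rule applies at each step is for the clinical team to decide.

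The cost is a protocol clarification and a site letter. No change to sample size or to the SAP's efficacy methods is needed.
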